1. Severe diabetes related chronic complications such as chronic renal failure, blindness, amputations, stroke, etc.
2. Concomitant chronic illnesses that would affect their participation in the program, i.e. cancer, debilitating diseases, etc.
3. Any other condition that would affect participant's basic mental health skills.
4. Type 1 diabetes or gestational diabetes.
5. Patients with abnormal hemoglobin, anemia or any condition that may affect red blood cell turnover. Any of these conditions may be detected through participants' history or through the laboratory report at study screening.
6. Signs or symptoms of metabolic decompensation (polyuria, polydypsia, polyphagia, unexplained weight loss, blurry vision, lethargy, etc.)

Elimination Criteria:

Development of any acute event during the study period that would affect participants' primary outcome at the discretion of the investigator, e.g. hyperosmolar coma, acute event of significant hyperglycemia or the use of certain medications like steroids.

Groups:

A total of 92 participants will be randomly assigned to one of the two study groups:

Group 1 – Intervention group – this group will complete activities described above. During scheduled follow-up clinical visits at months 3, 6, and 9, an additional A1c will be obtained. All measurements will be covered through the study grant if the patient does not have a recent laboratory result (2 weeks prior to the study visit) for the following test: A1c, lipid panel, ALT, AST, microalbumin, and chem 6 result.

Group 2 - Control Group –

This group will attend regular visits with their medical and education providers. As in the intervention group, these visits are expected to occur at 3, 6, and 9 months after the first visit. This group corresponds to the usual care that is provided at DHR.

Primary Outcome:

The primary outcome variable will be the change in hemoglobin A1c value from baseline to 6 months.

Sample Size:

We hypothesize that the decline in hemoglobin A1c value between the baseline and the six-month visit will be at least 0.5 percent greater in the intervention group than in the control group.

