The sample size and power calculation is based on preliminary results of our study where the study aimed at behavioral change. Assuming a mean reduction of 0.504 (SD= 1.2) in A1c in the intervention group and no change in the control group a sample size of 37 per group will be needed to detect this reduction with 80 % at 5% level of significance (one-sided) using the t-test. Assuming a 20% dropout, 46 study subjects per group (total 92) will be needed.

Recruitment:

Study Protocol

Study candidates will be identified at the partner site (DHR) where this protocol will take place. This will be done by creating flyers, videos, print and web-based ads, and letters to invite patients that attend the practice to join the study and/or by directly inviting patients that regularly attend the practice. Proper informed written consent will be obtained from all individuals prior to participation in the study.

Interventions:

a. Virtual diabetes self-management group

- i. Weekly conversations led by the diabetes educator (30-minute) using teleconsultation to deliver diabetes education and enhance adherence to treatment recommendations. These conversations will occur during the first 12 weeks of the intervention and will consist of the following elements: a) open question as to whether there is a particular item for discussion that the patient would like to address; b) review of blood glucose and physical activity results; c) review of the adherence to the four basic self-care behaviors (meal plan, physical activity, glucose monitoring and medications); d) identification of barriers to adhere to treatment recommendations; and e) provision of specific recommendations to overcome identified barriers. In order to provide diabetes education in a culturally and linguistically oriented manner, particularly to those patients with low health literacy, all participants in the virtual education program will be encouraged to listen to Rosa's or Jose's Story during the first 8 weeks of the intervention. These are audio-novellas developed by the Latino Diabetes Initiative at Joslin Diabetes Center to educate Latino patients with type 2 diabetes using the story telling method in a practical and engaging manner.

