Before any study procedure is done, the patient will be asked to read the consent form. A member of the study staff will discuss the study and the study procedures. Additional time from participants' regular clinical appointments will be necessary to collect study related information as follows:

Visit 1: This visit will last 60 minutes and will start by obtaining an A1c value to verify patient's eligibility. After a patient has been enrolled in the study (A1c value between 8-14%) they will be randomly assigned to the control or intervention group (virtual diabetes self-management education program using teleconsultation) and baseline information will be collected. Participants in the intervention group will be trained to use technology related to the teleconsultation, their own glucometer and the pedometer administered by this program.

Visit 2: This visit will last 60 minutes for questionnaires and will be completed 3 months after visit 1. All the tests and questionnaires detailed in table 1 will be administered at this visit.

Visit 3: This visit will last 60 minutes for questionnaires and will be completed 6 months after visit 1. All the tests and questionnaires detailed in table 1 will be administered at this visit.

Study Protocol

Visit 4: This visit will last 60 minutes for questionnaires and will be completed 9 months after visit 1. All the tests and questionnaires detailed in table 1 will be administered at this visit.

Timeline Table for Study Procedures:

Study Variables (both groups)	Baseline Visit	3	6	9
Laboratories				
Blood drawn	x	x	x	x
A1c	x	x	x	x
Lipid profile	x	x	x	x
ALT (from patient record if available)	x	x		x
AST (from patient record if available)	x	x		x
Microalbumin (from patient record if available)	x		x	x
Chem 6 (from patient record if available)	x	x		x
Measurements				
Weight	x	x	x	x
Height	x			
Blood pressure	x	x	x	x
Questionnaires				
Demographic characteristics	x			
Diabetes history	x			
Diabetes treatment plan	x	x	x	x
Adherence to prescribed drugs	x	x	x	x
Measures of emotional distress (depression, anxiety and PAID)	x		x	
Health literacy	x			
Self-care behaviors	x	x	x	x
Executive function	x			
Depression scale	x	x	x	x
Physical activity: pedometer use and number of steps per day	x	x	x	x
24 hour recall	x	x	x	x
Food frequency questionnaire	x	x	x	x
Analysis of the photo of the content of the refrigerator (only for the intervention group)	x	x	x	x

IRB:

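### The only analysis named, a t-test on the 6-month A1c change, would by default leave out the month-3 A1c of participants lost between months 3 and 6; a repeated-measures model would use it

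*Combined protocol and SAP*

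**What the plan says.** The Primary Outcome section fixes a single time point: "The primary outcome variable will be the change in hemoglobin A1c value from baseline to 6 months".

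The Sample Size section holds the only reference to a method of analysis. The calculation is made at the 5% "level of significance (one-sided) using the t-test". It concludes that "a sample size of 37 per group will be needed" and then allows for loss: "Assuming a 20% dropout, 46 study subjects per group (total 92) will be needed".

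The document has no analysis section, no definition of the analysis population, no intention-to-treat statement, no rule for missing A1c values and no repeated-measures model.

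A1c is nevertheless measured repeatedly. Under Study Visits, Visit 2 "will be completed 3 months after visit 1", and the Timeline Table for Study Procedures, which covers both groups, marks A1c at baseline and at 3, 6 and 9 months.

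**The concern.** Enrolling more people replaces lost numbers. It does not correct for who is lost. A participant who attends month 3 and then leaves has a post-baseline value of the primary variable in the database, and the named test has no use for it.

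A small loss of precision follows. The larger stake is selection. If those who leave after month 3 differ in early response from those who stay, and differ more in one arm, the two groups of completers are no longer comparable at month 6.

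A differential mechanism is possible here. Only the intervention arm has 12 weekly teleconsultations, 7 later calls and weekly texts. Its educators review glucose results with participants, and the contact changes from teleconsultation to tapering calls close to the month-3 visit. The documents do not show that such dropout will happen, nor in which direction.

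This is a different matter from retrieving a missing month-6 result, because the month-3 value is already held.

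**Working it through.** **Inputs from the documents.** Sample Size section: SD of change 1.2 (given for the intervention arm; assumed equal in control), effect 0.504, one-sided 5%, 37 needed and 46 enrolled per group, 20% dropout.

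**Assumed, because the documents do not say.** Correlation r between month-3 and month-6 change: 0.5 to 0.8. Timing of dropout: varied below.

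**The plan's own figure.** 37/0.8 = 46.25, stated as 46; 46 × 0.8 = 36.8, about 37. The dropout step holds, and it counts each dropout as contributing nothing. (Whether 37 gives the stated power in a two-group comparison is a separate question and is not relied on here.)

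**Precision.** With dropout unrelated to response, the variance of the month-6 mean using month 3, relative to completers only, is (1 − r²) + r² × n6/n3. Here n6 = 36.8 have month 6 and n3 have month 3.

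- All dropouts have month 3 (n3 = 46, n6/n3 = 0.8). At r = 0.5: 0.75 + 0.25 × 0.8 = 0.950. At r = 0.8: 0.36 + 0.64 × 0.8 = 0.872. The standard error falls by 1 − √0.950 = 2.5% to 1 − √0.872 = 6.6%, which is like having 38.7 to 42.2 completers instead of 36.8.
- Half of them have it (n3 = 41.4, n6/n3 = 0.889). The ratios are 0.972 and 0.929, and the standard error falls by 1.4% to 3.6%.

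**Bias of the completers contrast.** Let the log-odds of leaving after month 3 rise linearly with poor month-3 response, with a given slope per SD. Let m be the mean standardised month-3 change among those who stay, found by integrating over a standard normal. The bias is r × 1.2 × (difference in m between arms). For slope 1, m is 0.173 SD in the favourable direction at 20% loss and 0.100 at 11.1% loss. For slope 0.5 it is 0.096 and 0.054. At 11.1%, half of the 20% total is lost at random before month 3, and the remaining tenth of those randomised is 10/90 of those seen at month 3.

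The standard error of the contrast is 1.2 × √(2/36.8) = 0.280. The one-sided error rate with no true effect is 1 − Φ(1.645 − bias/0.280).

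| Case | Lost after month 3 | Slope, intervention / control | Bias at r = 0.5 / 0.7 / 0.8 | Error rate |
|---|---|---|---|---|
| A | 20% | 1 / 0 | 0.104 / 0.146 / 0.166 | 10% / 13% / 15% |
| B | 20% | 1 / 0.5 | 0.046 / 0.065 / 0.074 | 7% / 8% / 8% |
| C | 11.1% | 1 / 0 | 0.060 / 0.084 / 0.096 | 8% / 9% / 10% |
| D | 11.1% | 1 / 0.5 | 0.028 / 0.039 / 0.044 | 6% / 7% / 7% |
| E | 10% | log 1.5 / 0 | 0.024 / 0.034 / 0.038 | 6% / 6% / 7% |

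Worked cell, case A at r = 0.8: 0.8 × 1.2 × 0.173 = 0.166; 0.166/0.280 = 0.59; 1 − Φ(1.05) = 0.147.

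Simulation of cases A to D (46 per arm, 6,000 trials per cell) agrees: up to 0.169 and 15.4% in case A, and up to 0.077 and 8.2% in case B. A likelihood-type estimate that uses month 3 has bias within 0.01 and an error rate of 4.6% to 5.4% in all four. The sign is positive, favouring the intervention, when poor early responders leave that arm. It reverses if good responders leave.

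**The case against.** A reader might infer that the plan commits to a completers-only analysis and discards the month-3 values. The documents do not support that. The t-test appears only inside a sample-size calculation, and inflating enrolment for dropout does not define an analysis set. What can be said is that nothing else is specified, and that the one named test works that way by default.

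A reader might also take 0.10 to 0.17 as the expected bias. That is case A, which needs all dropout to fall after month 3, strong dependence on response in one arm and none in the other. None of this comes from the documents. Relaxing it brings the bias down several-fold.

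The mechanism can be questioned too. Stopping the educator contacts is not the same as missing the month-6 A1c. Visits coincide with regular care in both groups, recent laboratory results can stand in (stated under Groups for the intervention arm), and each completed visit is paid. This lowers the likely amount of differential loss but does not exclude it, since the plan itself expects 20%.

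Finally, the model is no full remedy. It rests on dropout depending only on observed values, and it cannot recover anyone lost before month 3, which is when the 12 weekly teleconsultations take place. If 10% of one arm left before month 3 with slope 1 on the unseen month-3 response (m = 0.091), and early loss in the other arm was random, a bias of r × 1.2 × 0.091, about 0.05 to 0.09, would remain.

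All four points stand as limits on size. None makes the t-test on completers the better choice.

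**Conclusion.** The point holds in a limited form. The plan names one method for the primary outcome. That method has no place for a participant without a month-6 value, although a month-3 A1c is scheduled in both arms, and the plan states no population or missing-data rule that would change this.

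The precision at stake is minor. Bias is the main reason to act. Cases B, D and E give the mild range of about 0.02 to 0.08 A1c points, roughly 5% to 15% of the assumed 0.504, with a one-sided error rate of about 6% to 9%. Case C lies just above it, at up to about 0.10. Case A sets the upper end at about 0.17, a third of the assumed effect, with an error rate of about 15%.

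All of these figures rest on the assumed correlation, timing and dependence on response. The bias is zero if dropout is unrelated to response, or related to it equally in both arms.

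**What to change.** Add to the Primary Outcome or Sample Size section:

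- The month-6 difference in A1c is estimated with a mixed model for repeated measures on the 3-, 6- and 9-month values, with arm by visit, baseline A1c by visit and an unstructured covariance.
- The model includes all randomised participants with at least one post-baseline A1c, and the month-6 contrast is primary.
- The completers t-test is a sensitivity analysis.
- The model is valid only if dropout depends on observed values, and it does not recover participants lost before month 3. Their number is reported by arm, and a sensitivity analysis examines departures from this assumption.

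The cost is analysis wording only: no new visits, measurements or participants. The downside is a model slightly more complex than a t-test.
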